6.3.3.4 Other non-hematologic toxicities

If a patient experiences other grade 3/4 non-hematologic toxicity, which is considered to be at least possibly related to midostaurin, midostaurin must be interrupted until toxicity resolves to

\leq grade 2. If midostaurin is held for more than 28 days, then discontinue midostaurin. Missed doses of midostaurin will not be made up.

Persistent grade 1 or 2 toxicities during maintenance therapy that patients may deem unacceptable may prompt drug holidays of as long as 28 days. No drug holidays longer than 28 days are allowed. Missed doses of midostaurin will not be made up.

6.3.4 Daunorubicin- dose modifications for hepatotoxicity

Initial and subsequent doses of daunorubicin should be modified as follows for hepatotoxicity:

Table 6-4 Daunorubicin hepatotoxicity dose modifications

Total bilirubin (mg/dl)	Daunorubicin Dose Modification
Grade $<$ 2	None
Grade \geq 2 and \leq 3	25% dose reduction
Grade $>$ 3	50% dose reduction

6.3.5 Cytarabine - dose modifications for neurotoxicity

For neurotoxicity \geq grade 2 due to cytarabine during consolidation therapy, discontinue cytarabine for the remainder of the cycle. Cytarabine may be considered at the next consolidation therapy cycle with a dose modification from 3 g/m² to 2 mg/m² or from 2 g/m² to 1 g/m² if the toxicity has resolved to \leq grade 1. For patient receiving 1 g/m², cytarabine may be discontinued at the discretion of the Investigator.

For a second occurrence of neurotoxicity \geq grade 2, high-dose cytarabine should be permanently discontinued.

Contributions of other concomitant medications to neurotoxicity should be assessed and medications discontinued if possible.

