5.2 Inclusion criteria

The Investigator or designee must ensure that only patients who meet all the following inclusion and none of the exclusion criteria are offered treatment in the study.

Inclusion Criteria:

Patients eligible for inclusion in this study have to meet **all** of the following criteria:

1. Written informed consent must be obtained prior to any screening procedures.
2. Patients must be 18 years of age or older at the time of signing informed consent.
3. Patients must have a documented unequivocal diagnosis of AML according to WHO 2008 classification. A bone marrow or blood blast count of $\geq 20\%$ is required, except for AML with t(15;17), t(8;21), inv(16) or t(16;16) where blast count may be $<20\%$, and, excluding M3 (acute promyelocytic leukemia).
4. Patients with secondary AML are eligible, e.g., patients with antecedent history of treatment for prior malignancy. AML patients with a history of antecedent treatment for myelodysplasia (MDS), e.g., azacitidine or decitabine, remain eligible for treatment on this study. These agents must have been discontinued for a period of at least 30 days or 5 half-lives of the drug (whichever is greater) before midostaurin can be administered.
5. Patients must have started “7+3” or “5+2” first induction chemotherapy regimen.
6. Patients must have a documented FLT3 mutation (ITD or TKD).).
7. Patients must have an ECOG Performance Status of ≤ 2
8. Patients requiring intrathecal chemotherapy must have a minimum washout of 48 hours prior to the first dose of midostaurin
9. Patients must have Total Bilirubin $\leq 2.5 \times$ ULN
10. Patients must have Serum Creatinine $\leq 2.5 \times$ ULN
11. Patients must be able to communicate well with the investigator to understand and comply with the requirements of the study
12. Women of child-bearing potential must have a negative pregnancy test before starting use of midostaurin.

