6.1.1 Dosing regimen

Table 6-1 Dose and treatment schedule – Induction

Treatment	Dose, route and frequency (based on 28-day cycles)
Standard-dose cytarabine* with anthracycline* (idarubicin or daunorubicin) (7+3)	Ara-C:100-200 mg/m ² /day by CIVI days 1-7 (168 hours infusion) daunorubicin: 60-90 mg/m ² /day by IV push on days 1-3 Or idarubicin: 12 mg/m ² /day by IV push on days 1-3
Cytarabine* with anthracycline* (idarubicin or daunorubicin) (5+2)	Ara-C:100 mg/m ² /day by CIVI days 1-5 daunorubicin 60 mg/m ² /day by IV push on days 1-2 Or idarubicin: 12 mg/m ² /day by IV push on days 1-2
Midostaurin	50 mg (two 25 mg capsules) twice a day by mouth on days 8-28 Patients should take their doses at approximately the same time each day, and approximately 12 hours should elapse between doses. Each daily should be given with food and a glass of water (~240 mL). Patients should be instructed to swallow capsules whole and not chew capsules. If vomiting occurs, no re-dosing is allowed before the next scheduled dose.

Table 6-2 Dose and treatment schedule – Consolidation

Treatment	Dose, route and frequency (based on 28-day cycles)
Cytarabine*	1-3 g/m ² infusion over 3 hours every 12 h on days 1, 3 and 5, up to 4 cycles based on age and per investigator discretion
Midostaurin	50 mg (two 25 mg capsules) twice a day by mouth on Days 8-28. Patients should take their doses at approximately the same time each day, and approximately 12 hours should elapse between doses. Each daily should be given with food and a glass of water (~240 mL). Patients should be instructed to swallow capsules whole and not chew capsules. If vomiting occurs, no re-dosing is allowed before the next scheduled dose.

Table 6-3 Dose and treatment schedule – Maintenance

Treatment	Dose, route and frequency (based on 28-day cycles)
Midostaurin	50 mg (two 25 mg capsules) twice a day by mouth on days 1-28, for 12 cycles or until relapse, unacceptable toxicity, or death. Patients should take their doses at approximately the same time each day, and approximately 12 hours should elapse between doses. Each dose should be given with food and a glass of water (~240 mL). Patients should be instructed to swallow capsules whole and not chew capsules. If vomiting occurs, no re-dosing is allowed prior to the next scheduled dose.

*Treatment formulation availabilities depend on countries marketing authorization as a local commercial supply is used.

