8.1 Adverse events

8.1.1 Definitions and reporting

An adverse event is defined as the appearance of (or worsening of any pre-existing) undesirable sign(s), symptom(s), or medical condition(s) that occur after patient's signed informed consent has been obtained.

Abnormal laboratory values or test results occurring after informed consent constitute adverse events only if they induce clinical signs or symptoms, are considered clinically significant, require therapy (e.g., hematologic abnormality that requires transfusion or hematological stem cell support), or require changes in study medication(s).

Adverse events that begin or worsen after informed consent should be recorded in the Adverse Events CRF. Conditions that were already present at the time of informed consent should be recorded in the Medical History page of the patient's CRF. Adverse event monitoring should be continued for at least 30 days following the last dose of study treatment. Adverse events (including lab abnormalities that constitute AEs) should be described using a diagnosis whenever possible, rather than individual underlying signs and symptoms. When a clear diagnosis cannot be identified, each sign or symptom should be reported as a separate Adverse Event.

Adverse events will be assessed and graded according to the CTCAE version 4.03.

If CTCAE grading does not exist for an adverse event, the severity of mild, moderate, severe, and life-threatening, death related to the AE corresponding respectively to Grades 1 - 5, will be used. Information about any deaths (related to an Adverse Event or not) will also be collected on a Death eCRF form.

The occurrence of adverse events should be sought by non-directive questioning of the patient (subject) during the screening process after signing informed consent and at each visit during the study. Adverse events also may be detected when they are volunteered by the patient (subject) during the screening process or between visits, or through physical examination,

laboratory test, or other assessments. As far as possible, each adverse event should be evaluated to determine:

1. The severity grade (CTCAE Grade 1-5)
2. Its duration (Start and end dates)
3. Its relationship to the study treatment (Reasonable possibility that AE is related: No, Yes)
4. Action taken with respect to study or investigational treatment (none, dose adjusted, temporarily interrupted, permanently discontinued, unknown, not applicable)

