**Table 2-2 Dose and treatment schedule – Consolidation**

Treatment	Dose, route and frequency (based on 28-day cycles)
Cytarabine	1-3 g/m  every 12 h on days 1, 3, 5 x up to 4 cycles based on age and per investigator discretion
Midostaurin	50 mg (two 25 mg capsules) twice a day by mouth on days 8-28

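### Two chemotherapy dose-modification rules are inconsistent as printed: a cytarabine step in Protocol 6.3.5 mixes g/m² and mg/m², and Protocol Table 6-4 lists grades under a bilirubin header in mg/dl

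*Protocol*

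**What the plan says.** **Cytarabine.** Protocol 6.3.5 applies after neurotoxicity of grade 2 or higher in consolidation. It stops cytarabine for the rest of the cycle and allows it to be considered again at the next one with a "dose modification from 3 g/m² to 2 mg/m² or from 2 g/m² to 1 g/m²", provided the toxicity has resolved far enough. The following sentence deals with patients already at 1 g/m². Protocol Table 6-2 gives the consolidation dose as "1-3 g/m ² infusion over 3 hours every 12 h on days 1, 3 and 5", and SAP Table 2-2 as "1-3 g/m 2 every 12 h on days 1, 3, 5".

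**Daunorubicin.** Protocol 6.3.4 introduces Table 6-4 with "Initial and subsequent doses of daunorubicin should be modified as follows for hepatotoxicity". The criterion column is headed "Total bilirubin (mg/dl" with the unit in brackets. All three rows beneath it are written as grades: below 2 (no change), 2 to 3 inclusive (25% reduction) and above 3 (50% reduction). Protocol 8.1.1 states that "Adverse events will be assessed and graded according to the CTCAE version 4.03". Table 6-4 does not refer to that scale, and neither document gives its cut-offs for bilirubin.

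**The concern.** Safety is the primary objective, and these are working instructions for what to give after toxicity. A rule that mixes units, or whose header and rows use different scales, can be applied differently at different sites.

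The analysis is touched in two modest ways.

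- Protocol section 12 permits no authorised deviations and requires significant ones to be reported, and SAP 2.5.4 lists deviations. Whether a site followed either rule cannot be judged until the text is settled.
- SAP 2.9.1 tabulates adverse events leading to reduction or interruption of treatment. The SAP counts cytarabine and the anthracyclines as study treatment, so actions under these rules may appear there.

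The planned summaries would not bring either problem to light. SAP 2.1.1 and 2.5.2 give cumulative dose and dose intensity for midostaurin, daunorubicin and idarubicin, but not cytarabine. SAP 2.5.2 tabulates dose changes with reasons for midostaurin only.

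**Working it through.** The plan states no statistical figure that depends on these rules, so there is nothing to reproduce. The check is a unit conversion and a side-by-side reading.

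**1. Cytarabine, Protocol 6.3.5**

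Inputs: first step 3 g/m² to 2 mg/m² and second step 2 g/m² to 1 g/m² (6.3.5); consolidation range 1-3 g/m² (Protocol Table 6-2, SAP Table 2-2).

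- First step as printed: 3 g = 3,000 mg, and 3,000 / 2 = 1,500. This is a 1,500-fold cut, or 1 − 2/3,000 = 99.93%.
- Second step as printed: 2 / 1 = 2. This is a 2-fold cut, or 50%.
- Printed first target against the lower end of Table 6-2: 1 g = 1,000 mg, and 1,000 / 2 = 500. The target is 500 times below the range.
- Continuity: the first step ends at 2 mg/m² and the second starts from 2 g/m², so the two do not connect.

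PDF extraction is an unlikely cause, because the other units in the same sentence read correctly. The Amendment 1 log lists only a renumbering for this section.

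**2. Daunorubicin, Protocol Table 6-4**

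| Row | Read as mg/dl | Read as grade | Reduction |
|---|---|---|---|
| 1 | below 2 | 0-1 | none |
| 2 | 2 to 3 | 2-3 | 25% |
| 3 | above 3 | above 3 | 50% |

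The header supports the first reading and the row labels support the second. The two would agree for every patient only if grade 2 began at exactly 2 mg/dl and the grades above 3 began just above 3 mg/dl. Neither document says so. The bilirubin values at which the readings diverge therefore cannot be worked out from the documents.

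The choice of row changes the daunorubicin total per induction cycle as follows (doses from Protocol Table 6-1):

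- 7+3, 60-90 mg/m²/day for 3 days: 180-270 mg/m² unreduced; × 0.75 = 135-202.5; × 0.50 = 90-135.
- 5+2, 60 mg/m²/day for 2 days: 120 mg/m² unreduced; × 0.75 = 90; × 0.50 = 60.

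These totals show what depends on the row. They do not show that any patient was placed in the wrong one.

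**3. Reach**

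Protocol Table 6-1 gives daunorubicin on days 1-3 or 1-2. Patients have already started chemotherapy when they are consented and screened between days 1 and 7 of that cycle, and midostaurin starts on day 8 (Protocol 4.1, 6.1 and 7.1.2). First-cycle daunorubicin is therefore largely given before the protocol can govern it. Protocol 7.1.4.1 allows a second induction cycle at the investigator's discretion and carries the first-cycle guidelines over to it. The rule thus mainly reaches patients who receive daunorubicin, not idarubicin, in a second cycle with raised bilirubin.

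**The case against.** The strongest reply is that these are two editorial faults with no demonstrated consequence.

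- **The cytarabine slip exposes itself.** It breaks with the second half of its own sentence, with the next sentence and with both dosing tables. Re-treatment is optional and follows only grade 2 or higher neurotoxicity. This stands, and it limits the point. It does not make the printed rule consistent.
- **Table 6-4 is a label mismatch, not two conflicting numbers.** Grade appears in every row, the protocol adopts one grading scale throughout, and its other grade-based dose rules do not cite that scale either. Failing to reprint the cut-offs is not itself a defect. This too stands. What remains is a header that names a concentration over rows that name grades, with cut-points that are plausible on either scale and nothing to say which governs.
- **The reach is narrow and treatment is over.** The SAP was revised after database lock, which follows the last patient's last visit, so no correction can change what was given. This is correct, and it moves the remedy to reporting and to any reuse of the text.
- **Much of the data is already due to be listed.** Protocol 10.3 lists all dosing data and summarises adjustments with reasons. That makes the remedy cheap, but a listing alone would not tell a reader that the rules were unclear.

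**Conclusion.** Both inconsistencies are in the current protocol text and should be corrected. The wording is certain; the consequences are not. The cytarabine target is 500 times below the lower end of the protocol's own range if taken literally. The Table 6-4 ambiguity decides between reductions of 0%, 25% and 50% for a group whose size the documents do not give. No hypothesis, sample size or analysis set is affected.

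A reader might infer more than the documents support:

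- *That patients received cytarabine in milligram doses.* The 500-fold figure measures the slip. Nothing in the documents shows that any site acted on it.
- *That the bilirubin limit for entry (2.5 × ULN, inclusion criterion 9) shows how many patients fall in a reduction row.* That criterion applies at screening, whereas the rule operates mainly at second induction. No passage re-applies the criterion there, and the documents give no ULN in mg/dl.
- *That the daunorubicin subgroups above and below 60 mg/m² in SAP 2.3 are distorted.* SAP 2.3 does not say which cycle's dose sets the category, and other departures from Table 6-1 can also fill the lower group. How that subgroup is defined is a separate matter from these two rules.

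The conclusion assumes that the printed text is what sites had. Any separate clarification to sites is not in the documents.

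**What to change.** 1. The sponsor's clinical team must reconcile Protocol 6.3.5 with Protocol Table 6-2 and SAP Table 2-2, and the header of Protocol Table 6-4 with its rows. Both texts should be corrected before any reuse. No dose or threshold is proposed here.
2. The clinical study report should disclose both inconsistencies.
3. From the dosing data already recorded (Protocol 6.6) and listed (Protocol 10.3), the report should give any cytarabine reductions for neurotoxicity and any daunorubicin reductions for hepatotoxicity, with the dose given.
4. It should add that the reading sites applied may not be identifiable. Protocol Table 7-1 leaves chemistry after screening to clinical need and the physician's discretion, so a bilirubin value may be missing, and a reduction that fits both readings identifies neither.

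The cost is a targeted review of existing listings, about one paragraph in the report and two text corrections. No patients, procedures or analyses of new data are added.

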6.3.6 Dose modification for obese patients

There is no clearly documented adverse impact of treatment of obese patients when dosing is performed according to actual body weight. Therefore, all dosing is to be determined solely by the patient's BSA as calculated from actual weight. This will eliminate the risk of calculation error and the possible introduction of variability in dose administration. The calculation is by the DuBois and DuBois formula: = 0.20247 x height (m)^{0.725} x weight (kg)^{0.425}

Failure to use actual body weight in the calculation of drug dosages will be considered a major protocol deviation. Investigators who are uncomfortable with administering chemotherapy dose based on actual body weight should not enroll obese patients on this study.

6.3.7 Anticipated risks and safety concerns of the study drug

Appropriate eligibility criteria and specific DLT definitions, as well as specific dose modification and stopping rules are included in this study. Recommended guidelines for prophylactic or supportive treatment for expected toxicities are provided in [Section 6.3.2](#) Refer to preclinical toxicity and or clinical data found in the [Investigator's Brochure Section 4.3 and Section 5].

6.3.8 Follow-up for toxicities

Patients whose treatment is interrupted or permanently discontinued due to an adverse event or laboratory abnormality above must be followed at least once a week (or more frequently if required by institutional practices, or if clinically indicated) during drug-hold and for 4 weeks, and subsequently at 4-week intervals, until resolution or stabilization of the event, or until the adverse event is considered permanent per investigators discretion, whichever comes first.

For adverse events and serious adverse events, patients will continue to be followed for toxicity for 30 days following the end of study treatment period.

6.3.8.1 Follow up on potential drug-induced liver injury (DILI) cases

Patients with transaminase increase combined with Total Bilirubin (TBIL) increase may be indicative of potential DILI, and should be considered as clinically important events.

The threshold for potential DILI may depend on the patient's baseline AST/ALT and TBIL value; patients meeting any of the following criteria will require further follow-up as outlined below:

- For patients with normal ALT and AST and TBIL value at baseline: AST or ALT $> 3.0 \times$ ULN combined with TBIL $> 2.0 \times$ ULN
- For patients with elevated AST or ALT or TBIL value at baseline: [AST or ALT $> 2 \times$ baseline AND $> 3.0 \times$ ULN] OR [AST or ALT $> 8.0 \times$ ULN], combined with [TBIL $> 2 \times$ baseline AND $> 2.0 \times$ ULN]

Medical review needs to ensure that liver test elevations are not caused by cholestasis, defined as ALP elevation $> 2.0 \times$ ULN with R value < 2 in patients without bone metastasis, or elevation of ALP liver fraction in patients with bone metastasis.

Note: (The R value is calculated by dividing the ALT by the ALP, using multiples of the ULN for both values. It denotes whether the relative pattern of ALT and/or ALP elevation is due to cholestatic (R ≤ 2), hepatocellular (R ≥ 5), or mixed (R > 2 and < 5) liver injury).

In the absence of cholestasis, these patients should be immediately discontinued from study treatment, and repeat LFT testing as soon as possible, preferably within 48 hours from the awareness of the abnormal results. The evaluation should include laboratory tests, detailed history, physical assessment and the possibility of liver metastasis or new liver lesions, obstructions/compressions, etc.

1. Laboratory tests should include ALT, AST, albumin, creatine kinase, total bilirubin, direct and indirect bilirubin, GGT, prothrombin time (PT)/INR and alkaline phosphatase.
2. A detailed history, including relevant information, such as review of ethanol, concomitant medications, herbal remedies, supplement consumption, history of any pre-existing liver conditions or risk factors, should be collected.
3. Further testing for acute hepatitis A, B, C or E infection and liver imaging (e.g. biliary tract) may be warranted.
4. Additional testing for other hepatotropic viral infection (CMV, EBV or HSV), autoimmune hepatitis or liver biopsy may be considered as clinically indicated or after consultation with specialist/hepatologist.

All cases confirmed on repeat testing meeting the laboratory criteria defined above, with no other alternative cause for LFT abnormalities identified should be considered as “medically significant”, thus, met the definition of SAE ([Section 8.2.1](#)) and reported as SAE using the term “potential drug-induced liver injury”. All events should be followed up with the outcome clearly documented.

6.4 Concomitant medications

The patient must be told to notify the investigational site about any new medications he/she takes after the start of the study treatment. All medications taken within 28 days prior to enrollment and all concomitant medications/therapies must be recorded on the Prior and Concomitant Medications eCRF. Anticancer agents (e.g. chemotherapy, radiation therapy, or biologic response modifiers or FLT3 inhibitors) other than those agents specified in this protocol are not permitted.

6.4.1 Permitted concomitant therapy

The patient must be told to notify the investigational site about any new medications he/she takes after the start of the study treatment. All medications (other than study drug) and significant non-drug therapies (including physical therapy, herbal/natural medications and blood transfusions) administered during the study must be listed on the Prior and Concomitant Medications or the Surgical and Medical Procedures eCRF.

6.4.1.1 Supportive care

In general, the use of any concomitant medication/therapies deemed necessary for patient supportive care and safety are permitted provided they are documented in the patient records.

6.4.1.1.1 Anti-emetic treatment with midostaurin

Nausea and vomiting are commonly reported in studies with midostaurin administration. These events are more frequent during combination therapy and are dose-dependent.

Prophylaxis for the prevention of nausea and vomiting is highly recommended. The kind and dose of anti-emetic drug should be chosen as per investigator discretion. Patients may be given ondansetron hydrochloride or granisetron. Other anti-emetics such as metoclopramide, methotripteneprazine, cyclizine, prochlorperazine or tropisetron may be used at the discretion of the investigator.

Since nausea (and in some cases vomiting) may still occur 1-3 hours after the dose, additional anti-emetics after midostaurin dosing may be required. In these cases, promethazine (phenergan), prochlorperazine (compazine), lorazepam (ativan) or other anti-emetics can be used $\frac{1}{2}$ hour to 1 hour after midostaurin as per investigator discretion.

If patients suffer from Grade 3 or 4 severe nausea and/or vomiting, refer to [Section 6.3](#).

